7.7.2 Statistical and Analytical Methods

A statistical analysis plan (SAP) describing the planned statistical analysis in detail with table, figure, and listing templates will be developed as a separate document.

Analyses will be primarily descriptive.

Descriptive summaries of continuous variables will include the number of observations, mean, standard deviation, median, range, and 95% confidence intervals (CIs) and/or inter-quartile range when appropriate. Descriptive summaries of categorical variables will include frequencies and percentages. Percentages will be based on the number of non-missing observations. Missing data will also be summarized.

Demographic and baseline characteristics of participants will be summarized using descriptive statistics.

The number and relative frequency of participants who prematurely discontinue participation in the study and reasons for discontinuation will be tabulated.

PAGE 33 OF 76

7.7.2.1 Evaluation of Primary Endpoint

The incidence of biliary diversion surgery, liver transplantation, or death will be assessed using descriptive statistics. Depending on the data available, event free survival endpoints will be summarized using the Kaplan-Meier method. Median time to event with 2-sided 95% CIs and the first and third quartiles will be reported. Survival curves will be presented as well. In addition, survival probability estimates at 6 months, 12 months, and then every 6 months and the associated 2-sided 95% CIs will be reported.

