7.3.1.1 Primary Endpoints

- Incidence of biliary diversion surgery, liver transplantation, or death in participants with ALGS chronically treated with odevixibat.
- Surgical biliary diversion-free survival, defined as time from the start of odevixibat treatment to the first occurrence of surgical biliary diversion or death.
- Liver transplant-free survival, defined as time from the start of odevixibat treatment to the first occurrence of liver transplant or death.
- Overall survival, defined as time from the start of odevixibat treatment to death.

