7.7.2.2 Evaluation of Secondary Endpoints

Safety data, including but not limited to the incidence of FSV deficiencies and their possible sequelae, the incidence of suspected hepatotoxicity requiring interruption of odevixibat treatment and bleeding events (including events requiring emergency department care, hospitalization, or blood transfusion), and growth and development (in the form of change in height and weight from baseline) will be collected, and descriptive statistics will be presented.

Adverse events will be coded according to MedDRA and will be classified by preferred term (PT) and system organ class (SOC). Adverse event listings will be presented by participant, SOC, and PT. All AEs and Special Situations will be included in the participant data listings.

The incidence of all reported AEs, serious and nonserious treatment-related AEs, all SAEs, all nonserious AEs, AEs leading to death, AEs leading to treatment discontinuation, and Special Situations will be tabulated separately. In addition, summary tables for AEs will be presented by severity and drug relationship (investigator-reported causality assessment). In addition, the incidence of all AEs associated with FSV deficiencies, and the incidence of all suspected hepatotoxicity requiring interruption of odevixibat treatment events and bleeding AEs (including events requiring emergency department care, hospitalization, or blood transfusion) will be tabulated.

Signs and symptoms of FSV deficiency will be summarized at each study visit using descriptive statistics. For each sign and symptom, the change from baseline by visit and the last assessment during treatment will be summarized by a shift table.

Change from baseline in growth (i.e. height [cm], weight [kg], body mass index [kg/m²], and corresponding Z-score [standard deviation from P50 standard growth curve]), will be summarized by visit for participants age < 18 using descriptive statistics.

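### The first primary endpoint (diversion, transplantation or death) is a percentage with no time horizon or time at risk, and the planned Kaplan-Meier analyses do not include this three-way event

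*Protocol*

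**What the plan says.** Protocol section 7.3.1.1 lists four primary endpoints without ranking them. The first is "Incidence of biliary diversion surgery, liver transplantation, or death in participants with ALGS chronically treated with odevixibat". The other three are times from the start of odevixibat: to diversion or death, to transplant or death, and to death.

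For the first endpoint, section 7.7.2.1 states: "The incidence of biliary diversion surgery, liver transplantation, or death will be assessed using descriptive statistics". Section 7.7.2 says what this means for a categorical outcome: "Descriptive summaries of categorical variables will include frequencies and percentages", and "Percentages will be based on the number of non-missing observations". An interval is named there only for continuous summaries ("median, range, and 95% confidence intervals (CIs) and/or inter-quartile range when appropriate").

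For the time-to-event endpoints, section 7.7.2.1 continues: "Depending on the data available, event free survival endpoints will be summarized using the Kaplan-Meier method", and "survival probability estimates at 6 months, 12 months, and then every 6 months and the associated 2-sided 95% CIs will be reported".

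Follow-up is unequal by design:
- Enrolment closes 3 years into a study of about 5 years (section 7.2.4).
- Participants who stop drug are followed for up to 180 days after the last dose (section 7.2.9).
- Follow-up also ends at withdrawal of consent, loss to follow-up (section 7.2.7) or entry into an interventional trial (section 7.2.8).
- Interim analyses are annual (section 7.7.4), each with its own report (section 10.1).

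**The concern.** A percentage of participants with an event is a risk only if everyone is observed over the same period. Here, one participant may contribute a few months and another 5 years. Someone who stops drug early and has a transplant after day 180 is counted as event-free. The non-missing rule does not settle whether a person lost at 6 months is event-free or excluded.

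The first primary endpoint could then not be read as a 1-, 2- or 5-year risk. It could not be compared between annual reports or set against another cohort with different follow-up. A rise from one report to the next could be taken for worsening outcome when it reflects only longer observation.

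**Working it through.** The protocol gives no sample size calculation, event rate or target figure, so there is no planned number to reproduce. The check asks what the percentage would show when the true risk is known.

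**Inputs from the protocol.** Enrolment over 3 years and data cut at about 5 years (section 7.2.4), so administrative follow-up runs from 2 to 5 years; exit 180 days after the last dose (section 7.2.9); annual cuts (section 7.7.4).

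**Assumptions, not in the protocol.** Uniform enrolment; constant event hazard h of 3%, 5% or 10% per year; discontinuation at a constant 0%, 10%, 25% or 40% per year, unrelated to risk.

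**True risk by time t:** 1 − exp(−ht). At h = 0.05: 1 − exp(−0.10) = 9.5% at 2 years and 1 − exp(−0.25) = 22.1% at 5 years.

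**Expected percentage at the final cut without discontinuation:** average 1 − exp(−ht) over t uniform from 2 to 5. At h = 0.05:

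1 − [exp(−0.10) − exp(−0.25)] / (0.05 × 3) = 1 − (0.9048 − 0.7788) / 0.15 = 16.0%.

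**With discontinuation,** by simulation:

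| Discontinuation per year | Followed under 2 years | h = 3% | h = 5% | h = 10% |
|---|---|---|---|---|
| 0% | 0% | 9.9% | 16.0% | 29.3% |
| 10% | 14% | 8.7% | 14.1% | 25.9% |
| 25% | 31% | 7.3% | 11.9% | 22.1% |
| 40% | 45% | 6.3% | 10.3% | 19.2% |
| True 2-year risk | | 5.8% | 9.5% | 18.1% |
| True 5-year risk | | 13.9% | 22.1% | 39.3% |

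Within each hazard column the risk to participants is the same in every row. Only the length of observation changes, and the percentage falls by roughly a third from top to bottom.

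**Across annual cuts at h = 0.05:**

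| Cut at year | 1 | 2 | 3 | 4 | 5 |
|---|---|---|---|---|---|
| No discontinuation | 2.5% | 4.8% | 7.1% | 11.7% | 16.0% |
| 25% per year | 2.4% | 4.5% | 6.3% | 9.5% | 11.9% |

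At year 1, for example, follow-up is uniform from 0 to 1 and the value is 1 − [1 − exp(−0.05)] / 0.05 = 2.5%. The figure rises about sixfold over the study (16.0 / 2.5 = 6.4) at constant risk.

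**Can the planned curves supply the missing risk?** At any time, the three-way risk is at least the larger of the diversion-or-death and transplant-or-death risks. It is at most their sum less the risk of death. Where it falls between these limits depends on how many participants have both procedures, which the curves do not show.

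**The case against.** The strongest reply is that the protocol speaks only of descriptive statistics. Its rule for categorical variables says what summaries will include, not that nothing else will appear, and detail goes to a separate SAP that is not shown. The same section also plans Kaplan-Meier curves and 6-monthly probabilities with 2-sided 95% CIs. Those cover every component: diversion and transplant each combined with death, and death alone. The word composite is never used, so the first endpoint might mean three incidences reported in turn, each with a related survival endpoint.

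Much of this stands, and it limits what can be claimed.
- A reader might infer that the primary outcomes have no analysis that handles censoring. The documents do not support that: three of the four primary endpoints are assigned one.
- A reader might infer that the absence of an interval for the proportion is an error. It is silence on something commonly left to the SAP. Intervals do matter at 30 to 45 participants (0/30 has an exact 95% upper limit of 11.6%, and 0/45 of 7.9%), but the omission is not a finding in itself.
- A reader might extend the point to section 7.7.2.2, where "The incidence of all reported AEs" and related summaries are to be tabulated. Tabulating AE incidence is conventional in a descriptive registry, and no error is shown there.

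What does not stand is the idea that the Kaplan-Meier plan cures the first endpoint. It is conditional on the data and does not include the three-way event. If three separate incidences are meant, each percentage still lacks a horizon.

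**Conclusion.** The point holds in limited form. Read together, sections 7.7.2 and 7.7.2.1 make the first primary endpoint a frequency and percentage with no horizon or time at risk, under follow-up that varies from about 6 months or less to about 5 years. Such a percentage estimates no defined risk. Of the four primary endpoints, it is the only one not assigned an analysis that handles censoring.

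At an assumed 5% per year it would be about 10% to 16%, against true risks of 9.5% at 2 years and 22.1% at 5 years. The size rests on assumed hazards and discontinuation rates, since the protocol gives neither. The direction does not depend on the particular values: the pattern is the same at 3% and 10% per year. That the figure is a plain percentage is the direct reading of the two sections together. The SAP could add to it, but the protocol wording does not require that.

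**What to change.** In section 7.7.2.1:

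1. Add time from the start of odevixibat to the first of diversion, transplantation or death to the Kaplan-Meier endpoints, with the same 6-monthly estimates and 2-sided 95% CIs.
2. Let participants who started odevixibat before enrolment, whom section 7.1 admits, enter the risk set only at enrolment (delayed entry). They must be alive and untransplanted to enrol, so earlier time would be event-free by selection. State how a diversion performed before enrolment is treated, since the exclusion criteria do not rule it out.
3. Report n/N with all analysed participants as the denominator and, beside it, events per 100 person-years from enrolment with an exact Poisson 95% CI. This stays usable if events are too few for Kaplan-Meier. For illustration, 3 events in 90 person-years is 3.3 per 100, with 95% CI 0.7 to 9.7.

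Both parts are needed. A rate alone gives a fixed-time risk only if the hazard is constant, and Kaplan-Meier may not be run if data are sparse.

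The cost is a wording change in section 7.7.2.1 and the SAP, and a few table columns. Treatment, surgery and death dates are already collected, so no new data are needed. Two limits remain. Early risk sets may be small if many participants are prior users. Both methods also assume that leaving follow-up is unrelated to risk, which exit 180 days after stopping drug may not satisfy.

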7.7.2.2 Evaluation of Secondary Endpoints

Safety data, including but not limited to the incidence of FSV deficiencies and their possible sequelae, the incidence of suspected hepatotoxicity requiring interruption of odevixibat treatment and bleeding events (including events requiring emergency department care, hospitalization, or blood transfusion), and growth and development (in the form of change in height and weight from baseline) will be collected, and descriptive statistics will be presented.

Adverse events will be coded according to MedDRA and will be classified by preferred term (PT) and system organ class (SOC). Adverse event listings will be presented by participant, SOC, and PT. All AEs and Special Situations will be included in the participant data listings.

The incidence of all reported AEs, serious and nonserious treatment-related AEs, all SAEs, all nonserious AEs, AEs leading to death, AEs leading to treatment discontinuation, and Special Situations will be tabulated separately. In addition, summary tables for AEs will be presented by severity and drug relationship (investigator-reported causality assessment). In addition, the incidence of all AEs associated with FSV deficiencies, and the incidence of all suspected hepatotoxicity requiring interruption of odevixibat treatment events and bleeding AEs (including events requiring emergency department care, hospitalization, or blood transfusion) will be tabulated.

Signs and symptoms of FSV deficiency will be summarized at each study visit using descriptive statistics. For each sign and symptom, the change from baseline by visit and the last assessment during treatment will be summarized by a shift table.

Change from baseline in growth (i.e. height [cm], weight [kg], body mass index [kg/m²], and corresponding Z-score [standard deviation from P50 standard growth curve]), will be summarized by visit for participants age < 18 using descriptive statistics.

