7 RESEARCH METHODS

7.1 Study Design

This will be a long-term, observational, prospective, and voluntary participation registry-based study designed to collect and assess real-world data on participants with ALGS chronically treated with odevixibat.

The study population will comprise participants with ALGS treated with odevixibat enrolled into the registry-based study. Participants who started odevixibat treatment before the implementation of the registry-based study may also be enrolled.

As this is an observational study designed to assess real-world data, the decision to prescribe the product must be taken prior to, and independently from, the willingness of the participant to be included in the registry-based study. This decision should be made in accordance with routine/standard clinical practice. The assignment of the participant to a particular therapeutic strategy is not decided in advance by the study protocol but falls within current practice.

Participants will be treated and monitored in accordance with usual medical practice during their participation in this registry-based study. No additional assessments or tests will be required by this protocol. All relevant data collected as part of routine medical care will be captured using the electronic Case Report Form (eCRF) by the investigator and transmitted to the sponsor. If some assessments included in this protocol are not routinely performed by the investigator, the corresponding sections in the eCRF do not need to be completed.

This registry-based study will collect data at Baseline and at each Follow-up Visit. Follow-up Visits are scheduled as per routine clinical practice (expected to occur at least every 6 months or more frequently, based on the investigator's judgement).

The duration of this registry-based study is approximately 5 years. Following enrolment, participants will continue to participate in the study for ≥ 2 years or until the time point of withdrawal of consent, for up to 180 days after last dose of odevixibat (in case of treatment discontinuation), death, the end of data collection, or the sponsor decides to discontinue the study.

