7.2 Setting

7.2.1 Inclusion Criteria

To be included in the registry-based study, the participant should fulfil the following inclusion criteria:

- (1) Diagnosed with ALGS.
- (2) On (or starting) active odevixibat treatment.
- (3) Signed informed consent and assent, as appropriate. Consent/assent from the participant or legal representative should be obtained, as appropriate, before any study data collection is conducted. Participants who turn 18 years of age (or legal age per country) while participating in the study will be required to provide consent for themselves.

PAGE 23 OF 76

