7.2.6 Study Schedule

The schedule of assessments that will be collected during the registry-based study is summarized in Table 1. As this is an observational study designed to assess real-world data, these assessments are not mandated by this protocol. If some assessments included here are not routinely performed by the investigator, the corresponding sections in the eCRF do not need to be completed. No additional assessments or tests will be required for the purpose of this study.

PROTOCOL: FINAL (WITH AMENDMENT #3): 10 DECEMBER 2024

PAGE 24 OF 76

 Table 1
 Schedule of Assessments

Assessment/Procedure	Baseline Visit Day 1	Follow up Visit(s) (as per routine clinical practice) ^{a,b}
Clinic visit	X	X
Informed consent ^c	X	-
Inclusion/exclusion criteria	X	-
Demographics and baseline characteristics ^d	X	-
Weight and height	X	X
Prior surgical procedures related to ALGS	X	-
General medical or surgical history	X	-
Prior medications ^e	X	-
Concomitant medications ^f	X	X
Concomitant vitamin supplementation ^g	X	X
Treatment with odevixibat (dates of treatment, dose, and changes/discontinuation)	X	X
Planned Biliary diversion surgery / Liver transplantation ^h	X	X
Biliary diversion surgery cancellation / Liver transplantation removal from listing	-	X
Clinical symptoms ⁱ	X	X
Laboratory parameters ^j	X	X
Concomitant surgical procedures	X	X
AEs and Special Situations ^k	X	X
Fat-soluble vitamin deficiency questionnaire ¹	X	X
Death report	-	X
Study discontinuation	-	X ^b

AE=adverse event; ALP=alkaline phosphatase; ALT=alanine aminotransferase; ALGS=Alagille syndrome; AST=aspartate aminotransferase; GGT=gamma-glutamyl transferase; INR=international normalized ratio; UDCA=ursodeoxycholic acid.

^a Follow-up Visits are expected to occur at least every 6 months according to routine clinical care or more frequently, based on the investigator's judgement. Investigators are encouraged to contact the participants (e.g., text-based reminders or phone calls to caregivers) to ensure follow-up visits are attended and to facilitate rescheduling, if necessary.

PROTOCOL: FINAL (WITH AMENDMENT #3): 10 DECEMBER 2024

PAGE 25 OF 76

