- ^b End of study for participants: the last Follow-up Visit as per routine clinical practice before the planned end of data collection (Section 4), withdrawal of consent, lost-to follow up, or 180 days after treatment discontinuation, whichever comes first. In case of treatment discontinuation, the last Follow-up Visit is recommended to happen onsite approximately 180 days after last dose of odevixibat.
- ^c If the participant is < 18 years of age (or the legal age of consent in the jurisdiction in which the study is taking place), assent and parent or legally authorized representative consent will also be required. Participants who turn 18 years of age (or legal age per country) while participating in the study will be required to provide consent for themselves.
- ^d Including age, sex, date of birth (MM/YYYY), and date of ALGS diagnosis
- ^e Prior medications refer only to medications related to the treatment of ALGS, including but not limited to rifampicin, UDCA and/or other IBAT inhibitors. Treatments used up to 9 months prior to the first odevixibat dose are to be collected (including the dose). If prior medications are discontinued, the date of discontinuation is to be provided. If the prior medication involves other IBAT inhibitors, any adverse events leading to their discontinuation will be documented, including their resolution.
- f Concomitant medications include ALGS and non-ALGS oriented treatments, including but not limited to rifampicin and/or UDCA.
- g Type and dose of to be collected.
- ^h Planned date and indication are to be collected.
- ¹ Includes pruritus and sleep disturbance, if (semi-) objective scoring data are available. For non-naïve participants, the most recent values prior to the first odevixibat dose are to be collected.
- ^j Laboratory parameters include-AST, ALT, ALP, total bilirubin, direct bilirubin, GGT, INR, albumin, creatinine, sodium, platelet count, and serum bile acid levels reported since the prior data collection. At the Baseline visit, historical (the most recent values in the last 9 months prior to the first odevixibat dose) values are also to be provided if available.
- ^k AEs collection begins once the informed consent has been signed and will end 180 days after the last odevixibat dose (unless consent was withdrawn). Special Situations include pregnancy or breastfeeding status and overdose, off-label use, misuse, abuse, occupational exposure, medication error, and lack of effectiveness (Section 9.1.3).

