- Clinical symptoms: pruritus and sleep disturbance, if (semi-) objective scoring data are available. For non-naïve participants: most recent values prior to the first odevixibat dose are to be collected.
- Planned biliary diversion surgery (planned date and indication)
- Listing for liver transplantation (planned date and indication)
- Laboratory parameters, including alanine aminotransferase (ALT), aspartate aminotransferase (AST), alkaline phosphatase (ALP), total bilirubin, direct bilirubin, gamma-glutamyl transferase (GGT), international normalized ratio (INR), albumin, creatinine, sodium, platelet count, serum bile acid levels, and FSV levels. Historical

PAGE 27 OF 76

values (the most recent values in the last 9 months prior to the first odevixibat dose) are also to be provided at baseline if available.

- FSV deficiency questionnaire
- Pregnancy or breastfeeding status

7.2.7.2 $Follow-up\ Visit(s)$

The participants will attend a clinic visit and assessments will be performed according to routine clinical care. For this registry-based study, the following variables will be captured from medical records as available:

Odevixibat and Concomitant Medications and Surgery Data Collection:

- Odevixibat dose (if changed/discontinued, provide date and reason)
- Concomitant medication (ALGS and non-ALGS oriented treatments, including but not limited to rifampicin, UDCA)
- Concomitant vitamin supplementation
- Concomitant surgical procedures (including but not limited to biliary diversion surgery (date, indication, and type of surgery) and liver transplantation (date and donor information))

Periodic Safety Data Collection:

- Adverse events (including suspected hepatotoxicity requiring interruption of odevixibat treatment and bleeding events) and Special Situation
- Weight and height
- Fat-soluble vitamins levels and FSV deficiency questionnaire
- Death (date and cause)

Periodic Effectiveness Data Collection:

- Laboratory parameters, including AST, ALT, ALP, total bilirubin, direct bilirubin, GGT, INR, albumin, creatinine, sodium, platelet count, and serum bile acid levels reported since the prior data collection
- Planned Biliary diversion surgery (planned date and indication)
- Listing for liver transplantation (planned date and indication)
- Cancellation of planned biliary diversion surgery and reason for cancellation
- Removal from listing for liver transplantation and reason for removal from the list

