7.3.2.5 Weight and Height

The registry-based study will assess growth and development (in the form of weight and height) for all participants at the Baseline Visit and at the Follow-up Visits (only if clinic visit) if available.

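### Height and weight have no pre-odevixibat look-back, so for participants already on treatment the change from baseline in growth starts mid-treatment and no SAP can recover the earlier part

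*Protocol*

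**What the plan says.** Section 7.1 opens the registry to prevalent users: "Participants who started odevixibat treatment before the implementation of the registry-based study may also be enrolled". Inclusion criterion 2 in Section 7.2.1 agrees: "On (or starting) active odevixibat treatment". Neither place limits how long a participant may have been treated before enrolment.

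Section 7.3.2.5 states that height and weight are assessed "for all participants at the Baseline Visit and at the Follow-up Visits (only if clinic visit) if available". Table 1 heads the first column "Baseline Visit Day 1" and places consent and the eligibility check in it, so this is the day of entry to the registry, which need not be the day of first dose.

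Other variables reach further back. Table 1 (laboratory footnote) asks that "historical (the most recent values in the last 9 months prior to the first odevixibat dose) values are also to be provided if available", and Sections 7.2.7.1 and 7.3.2.1 include fat-soluble vitamin (FSV) levels in that rule. For pruritus and sleep disturbance, Section 7.2.7.1 says: "For non-naïve participants: most recent values prior to the first odevixibat dose are to be collected".

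Growth is a secondary objective (Section 6.2.2) and a secondary endpoint (Section 7.3.1.2). Section 7.7.2.2 states that "growth and development (in the form of change in height and weight from baseline) will be collected, and descriptive statistics will be presented", and goes on to analyse it as change from baseline in height, weight, body mass index and Z-score, by visit, in participants under 18.

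**The concern.** A change from baseline describes growth under odevixibat only if baseline precedes odevixibat. For a child who starts the drug at entry, it does. For a child already on the drug, the first height and weight the registry holds are on-treatment values, so whatever happened between first dose and enrolment is missing from the change.

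The protocol sees this problem for laboratory values and symptoms and provides a look-back there. It provides none for height and weight, although a secondary endpoint depends on them. At stake is whether the reported growth change can be read as change since starting odevixibat. Because the gap lies in what is collected, the analysis plan cannot close it.

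**Working it through.** The protocol states no growth effect, standard deviation or power, so there is no figure to reproduce. The check is a comparison of sections followed by two short calculations.

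**1. Which variables have a value from before first dose?**

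| Variable | Value before first dose requested? | Where |
|---|---|---|
| Laboratory parameters | Yes, within 9 months, if available | Table 1 footnote; 7.2.7.1; 7.3.2.1 |
| FSV levels | Yes, same rule | Synopsis; 7.2.7.1; 7.3.2.1 |
| Pruritus and sleep scores | Yes, for participants already treated | Table 1 footnote; 7.2.7.1; 7.3.2.1 |
| Prior ALGS medication | Yes, up to 9 months | Table 1 footnote; 7.2.7.1 |
| Height and weight | No | Synopsis; Table 1; 7.2.7.1; 7.3.2.1; 7.3.2.5 |

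The look-back sentences sit inside the laboratory and symptom items and do not extend to height and weight. The protocol does not formally define baseline for the growth analysis. For a previously treated participant, though, the enrolment value is the earliest one requested, so it is the only possible baseline.

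**2. How much on-treatment time can go unrecorded?**

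Inputs: US authorization 13 June 2023 (Section 5.3); planned start of data collection November 2024 (Section 4); enrolment closes 3 years after start (Section 7.2.4).

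- June 2023 to November 2024: 12 + 5 = about 17 months.
- Enrolment close: November 2024 + 36 months = November 2027, so 17 + 36 = about 53 months.

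These figures apply to someone treated continuously since authorization. A later start of treatment shortens the gap, and exposure in an earlier trial lengthens it.

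**3. What could this do to a pooled mean change? (illustration)**

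Let D be the mean change since first dose, assumed equal in both groups; p the share of participants already treated at enrolment; and f the fraction of their change that occurred before enrolment. New starters contribute D and prior users contribute (1 − f)D, so

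pooled change = (1 − p)D + p(1 − f)D = D(1 − p × f).

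The share missed is p × f. The protocol gives neither quantity. Taking each between 0.25 and 0.75 as an assumption:

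- p = f = 0.25: 0.25 × 0.25 = 0.0625, about 6% missed.
- p = f = 0.50: 0.50 × 0.50 = 0.25, 25% missed.
- p = f = 0.75: 0.75 × 0.75 = 0.5625, about 56% missed.

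**The case against.** The strongest reply is that the asymmetry is deliberate. Section 7.3.2.7 lists biochemistry and symptoms as effectiveness variables, and for biochemistry it names changes from before to after odevixibat. Height and weight are collected as safety data. The objective is to evaluate growth in treated participants, and the endpoint is worded as standard-deviation scores without the word change. On-treatment Z-scores already compare a child with a growth reference and need no earlier value.

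Part of this stands: on-treatment Z-scores remain interpretable, and the concern is confined to the change-from-baseline summaries. But those summaries are what Section 7.7.2.2 plans. Nor is the look-back reserved for effectiveness: FSV levels are a safety variable in Section 7.3.2.6 and still receive the 9-month rule. The limitation acknowledged in Section 7.9, that routine data may be missing, does not cover values the protocol never asks for.

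Two stronger readings are tempting and are not supported:

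- *That growth cannot be placed on a time-on-treatment axis.* It can. The odevixibat start date is collected (Section 7.3.2.8) and visit dates must be in the source documents (Section 7.8.3). Only the segment before enrolment is missing.
- *That the protocol irrevocably pools two kinds of baseline.* It describes one summary with no split, but Section 7.7.2 leaves detail to the SAP and Section 7.7.3 allows subgroups there. A split would separate the two groups without restoring the earlier growth.

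Growth being listed first among the secondary endpoints carries no weight either. No hierarchy is set and no formal testing is planned (Section 7.9).

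**Conclusion.** The point holds as a data-collection gap. Following the protocol as written, change from baseline in growth starts mid-treatment for every previously treated participant, and change since treatment start cannot be reconstructed from the requested data. This rests on the text alone.

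The size is much less certain. The range of 17 to 53 months follows from the protocol's dates but describes a participant treated since authorization, and the inclusion criteria equally admit someone treated for a week. The range of 6% to 56% depends on assumed values of p and f and on equal total change in the two groups. A reader might infer that the entire response of prior users is lost. That is the boundary f = 1, where the missed share equals p, and nothing in the documents supports it. The documents also do not establish that growth responds early, so attenuation is conditional on that. The lack of a pre-treatment reference is not.

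With only 30 to 45 participants planned, even a moderate share of prior users could matter to the summary. The change is worth making and is inexpensive.

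**What to change.** In Sections 7.2.7.1, 7.3.2.1 and 7.3.2.5 and in Table 1 (with the matching synopsis list), request for previously treated participants the most recent height and weight before the first odevixibat dose, each with its date, if available. This mirrors the laboratory rule. The dates allow Z-scores to be calculated at the correct age.

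In Section 7.7.2.2, define the growth baseline as the last value on or before first dose, and report participants without such a value separately. Time windows and further subgroup detail can be left to the SAP.

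The cost is a few extra eCRF fields (two values and their dates) and a formal protocol amendment under Section 7.11. The values come from existing records, so no new assessment is needed and the observational design is unchanged. Some historical values will be missing, as for the laboratory data.
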